1.0 PROTOCOL SUMMARY AND/OR SCHEMA

Sarcomas comprise a very diverse group of malignancies including more than 50 subtypes of bone and soft tissue origin. Despite optimal approach, approximately 30-80% of patients will develop recurrent and metastatic disease after receiving initial therapy with curative intent. In this setting, responses to standard cytotoxic chemotherapy occur in 10-30% of the cases and median survival is 10-18 months.

Sarcomas are immunogenic neoplasms with a need for more therapeutic options. Prior immunotherapeutic agents have shown promise in select sarcoma patients. Using a combination of epacadostat, an IDO-1 inhibitor administered concurrently with the anti-PD1 monoclonal antibody pembrolizumab to treat patients with sarcomas and our planned scientific correlates, we believe we can assess the safety and efficacy of immune activating therapy and better understand the effects of combined therapy in antitumoral immune response.

This is an open-label, single-center, phase II study to evaluate the efficacy of epacadostat in combination with pembrolizumab in patients with locally advanced/metastatic, grade sarcoma (Figure 1. Study Schema). One treatment cycle will consist of 21 days. Patients will start both study drugs on day one of the first cycle. They will receive epacadostat 100mg, orally, twice daily, continuously for 21 days (Table 1). They will receive 200mg of pembrolizumab intravenously on day 1 of every three week cycle (Table 1). Patients will be reassessed with CT scans at week 8 and every 8 weeks thereafter. Treatment will be repeated until the patient develops progressive disease or unacceptable toxicity.

[figure not shown]
A total of 30 patients will be enrolled onto the study. Patients will be enrolled onto one of 4 cohorts. Each cohort will enroll a prespecified number of patients with certain sarcoma histological subtype(s). The 4 patient cohorts and the number of patients eligible to enroll per cohort in this study are as follows:

- A) Undifferentiated Pleomorphic Sarcoma (UPS), Liposarcoma (dedifferentiated or pleomorphic liposarcoma), or Myxofibrosarcoma (n=10)
- B) Leiomyosarcoma (n= 5)
- C) Vascular Sarcoma Subtypes (includingangiosarcoma ,and Epithelioid Hemangioendothelioma (EHE)) (n=5)
- D) Other (n=10)

Table 1 Study Treatment

Study Drug	Dose	Dose Frequency	Regimen/Treatment Period	Route of Administration
Epacadostat	100mg	Twice daily	Continuously days 1-21 of each 3 week cycle	Oral
Pembrolizumab	200mg	Every 3 weeks	Day 1 of each 3 week cycle	IV infusion

Figure 1. Study Schema

The hypotheses for this study include:

Primary hypothesis

1. Epacadostat given in combination with pembrolizumab, will ellicit an enhanced immune response in patients with advanced sarcoma with antitumoral effect, as assessed by RECIST 1.1.

Secondary hypotheses

- 1. Epacadostat, given in combination with pembrolizumab will be safe and well tolerated in patients with advanced sarcomas.
- 2. Epacadostat, given in combination with pembrolizumab, will improve progression free survival and overall survival in patients with advanced sarcoma as assessed by RECIST 1.1 and irRECIST.
- 3. Epacadostat, given in combination with pembrolizumab, will ellicit an enhanced immune response in patients with advanced sarcoma with antitumoral effect, as assessed by irRECIST.

Exploratory hypotheses

- 1. Baseline characteristics of the immune micorenvironment of sarcoma tumor tissue will vary depending on the sarcoma histological subtype.
- 2. Epacadostat given in combination with pembrolizumab, will alter immune related characteristics of tumor tissue in ways that may correlate with clinical outcome.
- 3. Epacadostat given in combination with pembrolizumab, will alter immune related characteristics of peripheral blood in ways that may correlate with clinical outcome
- 4. Epacadostat, given in combination with pembrolizumab, will benefit a substantial portion of patients with advanced sarcomas. Baseline tumor mutational burden and neoantigen production and and patient-specific immune characteristics,may correlate with clinical efficacy of the study therapy

2.0 OBJECTIVES AND SCIENTIFIC AIMS

Primary Objective:

To evaluate the efficacy of epacadostat in combination with pembrolizumab in patients with advanced sarcoma, as assessed by the best objective response rate (complete response+partial response) by 24 weeks using RECIST 1.1.

Secondary Objectives:

1) To assess the safety of epacadostat in combination with pembrolizumab in patients with advanced sarcoma using CTCAE v4.03 criteria for toxicity assessment.

- 2) To determine the progression free survival (PFS) rate at 24 weeks by RECIST 1.1 and irRECIST and overall survival (OS) for patients treated with epacadostat in combination with pembrolizumab.
- 3) To evaluate the efficacy of epacadostat in combination with pembrolizumab in patients with advanced sarcoma, as assessed by the best objective response rate (complete response + partial response) by 24 weeks by immune-related response evaluation criteria in solid tumors (irRECIST).

Exploratory Objectives:

- i) To determine the baseline characteristics of sarcoma tumors (pre-treatment biopsy sample) evaluated in this study including the level of IDO1, kynurenine and PD-1/PD-L1 expression, presence of tumor infiltrating lymphocytes (Tlls) and tumor antigens, gene expression profile, and the T-cell receptor clonality in tumor-infiltrating lymphocytes (TlL).
- ii. To assess the potential effect of epacadostat and pembrolizumab on selected biomarker expression measured in pre- and post-treatment tumor tissue and the association between these biomarkers (baseline level of expression and the change in biomarker level of expression following treatment) and clinical outcome, including characterization of IDO-1 expression, PD-1/PD-L1 expression, kynurenine expression, tumor infiltrating lymphocytes (Tlls) and tumor antigens, gene expression profiling, and characterization of T-cell receptor clonality in tumor-infiltrating lymphocytes (TlL).
- iii. To evaluate associations between selected biomarkers measured in serial peripheral blood and with clinical efficacy, including immunophenotyping and functional analyses, evaluation of serum levels of chemokines, cytokines and other immune mediators, and characterization of T-cell receptor clonality in peripheral blood.
- iv. To evaluate the association between baseline tumor mutational burden and neoantigen production with clinical efficacy of the study therapy.

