4.0 OVERVIEW OF STUDY DESIGN/INTERVENTION

4.1 Design

This is a single-center, phase II study to evaluate the efficacy of the 1001 inhibitor, epacadostat, given in combination with the anti-PD1 monoclonal antibody, pembrolizumab, for patients with metastatic and/or locally advanced grade sarcomas.

A total of 30 patients will be enrolled onto the study. Patients will be enrolled onto one of 4 cohorts. Each cohort will enrol a prespecified number of patients with certain sarcoma histological subtype(s). The 4 patient cohorts and the number of patients eligible to enrol per cohort in this study are as follows:

- A) Undifferentiated Pleomorphic Sarcoma (UPS), Liposarcoma (dedifferentiated or pleomorphic liposarcoma), or Myxofibrosarcoma (n=10)
- B) Leiomyosarcoma (n=5)
- C) Vascular Sarcoma Subtypes (including angiosarcomaEpithelioid Hemangioendothelioma (EHE))) (n= 5)
- D) Other (n=10)

This study will be conducted using a one-stage design. Patients will receive the recommended phase II dose (100mg bid) of epacadostat, when administered in combination with pembrolizumab. Epacadostat 100mg will be administered orally, twice daily, continuously for 21 days. Pembrolizumab will be administered at a dose of 200mg every 21 days (±3 days). Treatment with epacadostat and pembrolizumab will start on day 1 of the first cycle. Each cycle will consist of 21 days.

Patients will be evaluated radiographically at baseline, week 8 (+/- 7 days) and every 8 weeks(+/- 7 days) subsequently until week 56 and then every 12 weeks thereafter or as per the discretion of the treating investigator. Response will be assessed using RECIST v1.1 (primary response assessment) and immune-related response evaluation criteria of solid tumors (irRECIST) (secondary response assessment).

All study participants where feasible will undergo mandatory tumor biopsies at baseline and week 7. Optional biopsies at progression will be offered. Biopsies must be collected within +/- 7 days of the originally scheduled timepoint. Serial blood samples will be obtained at baseline, during, and at the end of study treatment.

Study therapy should continue once there is no evidence of progression of disease per RECIST 1.1, no clear clinical deterioration and the patient is able to tolerate the treatment. Treatment beyond progression will be allowed at the discretion of the clinical investigator

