9.3 Duration of Therapy

Study treatment may continue until one of the following criteria applies:

Until a total of 35 cycles (approximately 2 years) of treatment has been administered as long as subjects are receiving benefit from treatment and have not had disease progression or met any criteria for study withdrawal outlined below

Clinical or radiographic disease progression as defined by RECIST 1.1. Patient may be allowed to continue treatment after progression if they are deriving clinical benefit (section 9.4).

Intercurrent illness that prevents further administration of treatment

Intolerance of study treatment

Patient decides to withdraw from the study

Physician decides to withdraw a patient from the study for a reason not listed here

Pregnancy in patient

The patient is lost to follow-up

Inability of the patient to comply with the requirement of the protocol for treatment or evaluation.

End of study, whichever occurs first.

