12.10 Progression-Free Survival (PFS)

PFS is defined as the period from start of study treatment until recurrent or progressive of disease (POD) is objectively documented (taking as reference for progressive disease the smallest measurement recorded on study), death, or date of last study visit involving assessment of disease status.

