12.11 Overall Survival (OS)

OS is defined as the observed length of life from start of study treatment to death or the date of last contact.

12.12 Secondary Response Criteria - Immune-related Response Evaluation Criteria in Solid Tumors (irRECIST)

In 2013, Nishina et al. demonstrated that immune-related response criteria using unidimensional measurements were highly concordant with the bidimensional results of irRC, but with less measurement variability. ⁵⁵ Based on these findings and in order to utilize both the established criteria of irRC and RECIST 1.1, the two systems have been adapted, modified, and combined into the Immune-related Response Evaluation Criteria in Solid Tumors (irRECIST). The adapted irRECIST criteria are modifications to the irRC, incorporating the findings of Nishina et al. and the advantages of RECIST 1.1 while overcoming the shortcomings of each of the other guidelines.

irRECIST

Immune-related RECIST (irRECIST) guidelines according to Bohnsack et al. are presented below.

I. Baseline Assessments in irRECIST

In irRECIST, baseline assessment and measurement of measurable/non-measurable and target/non-target lesions and lymph nodes are in line with RECIST 1.1.

One new definition is added: If a subject has no measurable and no non-measurable disease at baseline the radiologist will assign 'No Disease' (irND) as the overall tumor assessment for any available follow-up time points unless new measurable lesions are identified and contribute to the total measured tumor burden (TMTB). irND is a valid assessment in studies with adjuvant setting where the protocol and study design allow the inclusion of subjects with no visible disease

Follow-up Assessments in irRECIST

A. Follow-up recording of target and new measurable lesions

The key difference in irRECIST is that the appearance of new lesions does not automatically indicate progression. Instead, all measured lesions (baseline-selected target lesions and new measurable lesions) are combined into the total measured tumor burden (TMTB) at follow up. Baseline-selected target lesions and new measurable lesions are

NOT assessed separately. Measurements of those lesions are combined into the TMTB, and one combined assessment provided.

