Upon permanent discontinuation from the study treatment for any reason, the following procedures will be performed approximately 30 (+7) days after the last dose of epacadostat or the last dose of pembrolizumab, whichever is later.

Full medical history, physical exam, assessment of performance status by KPS or ECOG status

Review of concomitant medications

Complete vital signs (pulse, blood pressure, temperature, respiratory rate, oxygen saturation) as well as weight and height. Height may be documented at any time prior to registration.

12-lead electrocardiogram (ECG)

Serum -HCG or urine pregnancy test for women with child-bearing potential. If the urine test is positive or cannot be confirmed as negative, a serum pregnancy test will be required.

Complete blood count with differential, including lymphocyte and eosinophil count.

Comprehensive metabolic panel (glucose, blood urea nitrogen, creatinine, sodium, potassium, chloride, bicarbonate, calcium, total protein, albumin, serum bilirubin, alkaline phosphatase, ASL, AST) phosphorus, magnesium

TSH, T4 free, T3

Amylase and lipase

An optional biopsy will be offered at progression of disease.

Patients whose treatment is interrupted or permanently discontinued due to an adverse event or clinically significant laboratory value must be followed until resolution or stabilization of the event.

Reporting of adverse events will occur for up to 90 days for serious adverse events (within 90 [+7] days after the last administration of epacadostat or pembrolizumab, whichever is later), Events of Clinical Interest (within 90 [+7] days after the last administration of epacadostat or pembrolizumab, whichever is later), and documentation of concomitant medications.

Long-Term Follow-up Procedures:

All subjects who permanently discontinue study drug for any reason other than withdrawal of full consent will be contacted by clinic visit or telephone to assess survival and initiation of additional sarcoma therapy. Contact for all subjects will be attempted every 12 weeks (±28 days) following the safety follow-up visit until death, subject withdraws full consent, or up to 12 months after the end of treatment.

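### 24-week PFS by irRECIST is only partly observable: patients who stop at RECIST 1.1 progression without irPD have no required later scan, and the plan gives no rule for them

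*Combined protocol and SAP*

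**What the plan says.** - **Objective and estimator.** Secondary objective 2 in section 2.0 is "To determine the progression free survival (PFS) rate at 24 weeks by RECIST 1.1 and irRECIST". Section 14.2 estimates it by Kaplan-Meier and sets no target rate.
- **Two criteria.** Under 12.3.1.1 any new lesion is RECIST 1.1 progression. In 12.12, "The key difference in irRECIST is that the appearance of new lesions does not automatically indicate progression". New measurable lesions are added to the total tumor burden. irPD needs a rise of at least 20% and 5 mm from nadir, or massive, unequivocal worsening of non-target or new non-measurable disease.
- **Treatment at progression.** Section 9.3 lists "Clinical or radiographic disease progression as defined by RECIST 1.1" among the criteria that end treatment, but its next sentence lets a benefiting patient go on. Section 4.1 says "Treatment beyond progression will be allowed at the discretion of the clinical investigator". Sections 9.4 and 13.0 make this conditional on the treating physician's judgment of benefit and tolerance, and 12.1 lets the investigator continue until progression is confirmed. Section 12.12 foresees further irRECIST assessments when treatment continues. Section 1.0 gives the rule without the exception: "Treatment will be repeated until the patient develops progressive disease or unacceptable toxicity".
- **After stopping.** Table 5 marks no CT or MRI at the off-study visit, and the end-of-study procedures in 13.0 list no imaging. In long-term follow-up patients are "contacted by clinic visit or telephone to assess survival and initiation of additional sarcoma therapy".
- **PFS definition.** Section 12.10 gives one definition for both criteria: time to documented progression, "death, or date of last study visit involving assessment of disease status". Neither 12.10 nor 14.2 has an event or censoring rule specific to irRECIST.

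**The concern.** Take a patient with a new lesion at week 8 whose total burden has risen by less than 20%. That is RECIST 1.1 progression but not irPD. If treatment stops there, the plan requires no later scan, so irPD can no longer be documented. The last disease assessment is the scan that showed RECIST progression, and the patient leaves the irRECIST risk set on that date without an event.

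Kaplan-Meier then gives this patient the later prognosis of those still being scanned. Yet continuation is reserved for patients judged to be benefiting, so those who stop were probably doing worse. If so, the irRECIST rate is too high.

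What is at stake is interpretation. Secondary hypothesis 2 concerns PFS by both criteria. An irRECIST rate above the RECIST 1.1 rate invites a reading of delayed immune benefit, although part of the gap may come from patients whose later course was never observed.

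**Working it through.** **The plan's own figures.** None exists for 24-week PFS by either criterion. The only design figure is for response rate (14.1): at least 6 responses in 30, 10% against 30%. The exact binomial gives a type I error of 0.0732 and power of 0.9234. These match the stated 0.07 and 92%, and this point does not affect them.

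**Inputs.** From the documents: 30 patients; scans at weeks 8, 16 and 24; Kaplan-Meier. Assumed, because the documents give no counts: RECIST 1.1 progression in 12, 5 and 3 patients at the three scans; a fraction f of these is RECIST-only (no irPD); every RECIST-only patient stops and is censored at that scan. Counts are expected values and so can be fractional.

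**Numbers at risk.** 30, then 30 - 12 = 18, then 18 - 5 = 13, leaving 10 at the end.

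**RECIST 1.1 rate.** (1 - 12/30)(1 - 5/18)(1 - 3/13) = 10/30 = 33.3%.

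**irRECIST Kaplan-Meier.** S = (1 - 12(1-f)/30) × (1 - 5(1-f)/18) × (1 - 3(1-f)/13).
- f = 0.2: 0.680 × 0.778 × 0.815 = 43.1%
- f = 0.4: 0.760 × 0.833 × 0.862 = 54.6%

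**Range of the true irRECIST rate.** The 20(1-f) irPD events are fixed. What is unknown is the later course of the 17f patients who stopped at week 8 or 16. Those who stop at week 24 are irPD-free at that time by definition.
- None of the 17f has irPD or dies by week 24: true rate = 1 - 20(1-f)/30.
- All of them do: true rate = 1 - [20(1-f) + 17f]/30.

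| f | Kaplan-Meier | True, none | Error (points) | True, all | Error (points) |
|---|---|---|---|---|---|
| 0.2 | 43.1% | 14/30 = 46.7% | -3.6 | 10.6/30 = 35.3% | +7.8 |
| 0.4 | 54.6% | 18/30 = 60.0% | -5.4 | 11.2/30 = 37.3% | +17.2 |

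**What Kaplan-Meier assumes.** It credits a patient who stops at week 8 with a chance of being irPD-free at week 24 of 0.778 × 0.815 = 63% (f = 0.2) or 0.833 × 0.862 = 72% (f = 0.4). The error is upward if those who stop do worse than the patients still followed, and downward if they do better.

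**Counting them as events.** If those who stop count as events on the RECIST progression date, this example returns 33.3% for any f. That is just below the lowest possible true rate (35.3% or 37.3%), so the figure is conservative.

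**A second model.** Assume an irPD or death risk of 20% or 30% per 8-week interval and RECIST-only progression in 5% to 15% per scan. If all RECIST-only patients stop, the error in points depends on their later risk per interval:
- equal to the others: 0
- half that of the others: -1 to -5
- 50%: +2 to +9
- 80%: +4 to +15

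If half continue and are scanned, the upward error falls to about +1 to +6. If all continue, it is essentially zero. The half-continue case gives continuers and those who stop the same later risk. Selecting continuers for benefit would weaken that reduction.

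**The case against.** The strongest objection is that the protocol does not end treatment or scans at RECIST 1.1 progression. Sections 4.1, 9.3, 9.4, 12.1 and 13.0 all allow treatment to continue, 12.12 plans irRECIST assessments in that setting, and no sentence ends the 8-weekly scans at RECIST progression. A reader might infer that irRECIST PFS cannot be observed at all; the documents do not support that. What remains is that continuation is discretionary and tied to perceived benefit, and that no imaging is listed for patients who stop. The instruction in 12.7 to keep trying to document progression applies to symptomatic deterioration without objective progression, not to these patients.

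A reader might also take the whole gap between 33% and 43% to 55% as bias. It is not. irRECIST is meant to be more lenient on new lesions, so part of the gap is a difference between criteria. Nor is upward bias built in, since the working shows both signs.

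Three further points stand in part. First, some patients with new lesions meet irPD on the same scan, so the affected group may be small. Second, 12.10 lists death as an endpoint and survival is followed for up to 12 months, so later deaths may enter as events; but the text does not say whether a death after the last scan counts, and irPD before death would still be missed. Third, this is a secondary single-arm estimate with no decision rule, and with 10 of 30 event-free the exact 95% interval is 17% to 53%. That limits the consequence, but a wide interval does not correct a systematic error.

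**Conclusion.** The concern holds in a limited form. The 24-week irRECIST PFS rate is only partly observable, and the plan does not say how to treat patients who stop at RECIST 1.1 progression without irPD. Censoring them at that scan is the natural reading of 12.10, though the section never uses the word.

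The censoring is probably informative and probably biases the rate upward, because continued scanning follows perceived benefit. In the worked example the error lies between about -4 and +8 points at 20% RECIST-only progression, and between about -5 and +17 at 40%. Those ranges rest on assumed counts and on every RECIST-only patient stopping; they shrink as more patients continue with scans. The documents fix neither the sign nor the size. The primary endpoint is not affected.

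**What to change.** In 12.10 and 14.2:

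1. Report how many patients stop at RECIST 1.1 progression without irPD and without a later scan.
2. Give the 24-week irRECIST PFS rate twice: with these patients censored at their last scan, and with them counted as events on the RECIST 1.1 progression date. The second is best shown alongside the first rather than as the sole definition, because it mixes the two criteria.
3. State that deaths found in survival follow-up count as PFS events.
4. State that an irRECIST rate above the RECIST 1.1 rate will not be read as delayed benefit unless the gap persists in the event-counted version. A gap that persists there rests on patients who were scanned again.

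Section 1.0 should also be reconciled with 4.1, 9.3 and 9.4 on treatment after progression, since it omits the exception they state.

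The cost is one extra Kaplan-Meier run and a few lines of text, with no added visits or patients. The event-counted figure is conservative and will look less favourable.
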